- f. The "Since Last Visit" C-SSRS form will be completed at all visits.
- g. Adverse events (serious and non-serious) and concomitant medications should be recorded from the time of signing the ICF through the subject's last visit.
- h. For women of childbearing potential only. All positive urine pregnancy test results must be confirmed by a serum test. Pregnancy tests can be performed at any time during the trial at the discretion of the investigator if pregnancy is suspected. Monthly pregnancy tests will be required for all women of childbearing potential.
- i. The urine drug screen can be conducted at any time during the trial at the discretion of the investigator.
- j. With subjects maintaining their normal BID dosing routine, a single daytime blood sample for determination of plasma CVL-865 concentration will be collected at Visits 5, 8, and 11. The date and time of the PK sample, as well as the time of ingestion of the morning dose of IMP (on the same day), will be recorded in the source documentation.
- k. One 5-mL sample for each adjunctive AED collected at Visits 5, 8, and 11.

**Table 3 Schedule of Assessments - Maintenance Phase (Visits 13 Through 15/ET Only), Taper Phase, and Post-treatment Follow-up Phase**

Trial Period/ Phases	Maintenance Phase (52 weeks) Visits 13 through 15/ET			Taper Phase (3 weeks)			Post-treatment Follow-up	
	Visit 13 b	Visit 14 b	Visit 15/ET c	Contact	Contact	Visit 16 b	Contact	Visit 17
Visit/Contact a	Visit 13 b	Visit 14 b	Visit 15/ET c	Contact	Contact	Visit 16 b	Contact	Visit 17
Day	323	351	379	386	393	400	407	428
Week	46	50	54	55	56	57	58	~61
Window	± 3 days							
Entrance and History								
Review of birth control methods	X	X	X	X	X	X	X	X
Efficacy Assessments								
Review eDiary including compliance with use of eDiary	X	X	X	X	X	X	X	X
PGI-C			X					
CGI-S			X					
Safety Assessments								
Physical/neurological examination d			X			X		
ECG			X			X		
Vital sign measurements			X			X		
C-SSRS e			X			X		X
mCIWA-B			X	X	X	X	X	X
Prior/concomitant treatments including BZD use f	←-----→							
Adverse event monitoring f	←-----→							
Laboratory								
Safety laboratory blood sample	X	X	X			X		X
Safety laboratory urine sample			X			X		
Urine pregnancy test g	X	X	X			X		

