- g. For women of childbearing potential only. All positive urine pregnancy test results must be confirmed by a serum test. Pregnancy tests can be performed at any time during the trial at the discretion of the investigator if pregnancy is suspected. Monthly pregnancy tests will be required for all women of childbearing potential.

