#### Follow-up Period:

Follow-up telephone contact will be performed  $7\pm3$  days after the last dose of IMP. A Post-treatment Follow-up Visit will be made approximately 4 weeks after last dose of IMP.

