#### 4.4 Definition of Completed Subject

A subject is considered to have completed the trial if he/she has completed all phases of the trial including the last scheduled procedure (ie, Visit 17 assessments) as shown in the Schedules of Activities ([Table 2](#) and [Table 3](#)).

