## **7.3 Individual Subject Discontinuation**

After treatment assignment, a subject may stop treatment permanently for a variety of reasons. Treatment discontinuations may be initiated by a subject who is not satisfied with treatment or may become medically necessary due to AEs, required treatment with a disallowed medication or therapy, or other issues, as determined by the investigator.

Subjects should begin the Taper Phase at the time the decision is made to discontinue. All Taper Phase and Post-treatment Follow-up procedures should be performed as indicated in the Schedules of Assessments ([Table 2](#) and [Table 3](#)). Under certain circumstances, when subjects leave the trial early, dosing with the taper medication or continuing with the taper phase medication may be inadvisable. The decision not to taper the subject is upon agreement from the medical monitor. If the taper will not be utilized, then all assessments required at Visit 17 should be conducted approximately 30 days following the last dose.

For subjects who early terminate prior to Day 15 (prior to the Maintenance Phase), an alternate taper scheme may be used. This includes subjects who sign consent for CVL-865-SZ-002 but who are then determined to not meet eligibility criteria.

A subject will discontinue IMP for the reasons listed below:

- Any of the following AESIs

- Hemoglobin <8 g/dL
- WBC count <2.5 × 10^9/L
- Neutrophil count <1.5 × 10^9/L
- Platelet count <100 × 10^9/L
- Female subjects who have a positive pregnancy test result during the trial
- Withdrawal of consent
- Investigator's discretion (eg, including failure to comply with trial procedures or dosing)

All subjects have the right to withdraw their consent from further participation in the trial at any time without prejudice. Subjects cannot withdraw consent for use of data already collected as part of the trial, but only for future participation. The investigator can also discontinue a subject's participation in the trial at any time if medically necessary. Unless the subject provides their written withdrawal of consent or there is other written documentation by the investigator confirming the subject's verbal intent to completely withdraw from the trial, subjects should be followed for all protocol-specified evaluations and assessments, if possible.

Complete withdrawal of consent requires a subject's refusal of ALL of the following methods of follow-up:

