#### **8.4.5     *Pregnancy***

Details of all pregnancies in female subjects and female partners of male subjects will be collected after the start of IMP and until the final contact at Visit 17. At a minimum, monthly pregnancy tests will be completed throughout the trial for all women of

childbearing potential. During periods where monthly visits are not scheduled, female subjects can choose to visit the site for the test or complete the test via a remote option.

If a pregnancy is reported, the investigator should inform the medical monitor within 24 hours of learning of the pregnancy and should follow the procedures outlined in [Section 10.4](#) (Appendix 4).

Abnormal pregnancy outcomes (eg, spontaneous abortion, fetal death, stillbirth, congenital anomalies, ectopic pregnancy) are considered SAEs.

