- j. With subjects maintaining their normal BID dosing routine, a single daytime blood sample for determination of plasma CVL-865 concentration will be collected at Visits 5, 8, and 11. The date and time of the PK sample, as well as the time of ingestion of the morning dose of IMP (on the same day), will be recorded in the source documentation.
- k. One 5-mL sample for each adjunctive AED collected at Visits 5, 8, and 11.

Table 10. Maintenance Phase (Visits 13 Through 15/ET Only), Taper Phase, and Post-treatment Follow-up Phase

Trial Period/ Phases	Maintenance Phase (52 weeks) Visits 13 through 15/ET			Taper Phase (3 weeks)			Post-treatment Follow-up	
	Visit 13 ^b	Visit 14 ^b	Visit 15/ET ^c	Contact	Contact	Visit 16 ^b	Contact	Visit 17
Visit/Contact ^a	Visit 13 ^b	Visit 14 ^b	Visit 15/ET ^c	Contact	Contact	Visit 16 ^b	Contact	Visit 17
Day	323	351	379	386	393	400	407	428
Week	46	50	54	55	56	57	58	~61
Window	± 3 days							
Entrance and History								
Review of birth control methods	X	X	X	X	X	X	X	X
Efficacy Assessments								
Review eDiary including compliance with use of eDiary	X	X	X	X	X	X	X	X
PGI-C			X					
CGI-S			X					
Safety Assessments								
Physical/ neurological examination ^d			X			X		
ECG			X			X		
Vital sign measurements			X			X		
C-SSRS ^e			X			X		X
mCIWA-B			X	X	X	X	X	X
Prior/concomitant treatments including BZD use ^f	←-----→							
Adverse event monitoring ^e	←-----→							
Laboratory								
Safety laboratory blood sample	X	X	X			X		X
Safety laboratory urine sample			X			X		

Trial Period/ Phases	Maintenance Phase (52 weeks)			Taper Phase (3 weeks)			Post-treatment Follow-up	
	Visits 13 through 15/ET			Contact	Contact	Visit 16 ^b	Contact	Visit 17
Visit/Contact ^a	Visit 13 ^b	Visit 14 ^b	Visit 15/ET ^c					
Day	323	351	379	386	393	400	407	428
Week	46	50	54	55	56	57	58	~61
Window	± 3 days							
Urine pregnancy test ^f	X	X	X			X		
Other								
IMP dispensing			X					
Collect final eDiary device								X
IMP compliance assessment	X	X	X	X	X	X		
AED compliance assessment	X	X	X	X	X	X	X	X

Abbreviations: AED = antiepileptic drug; BZD = benzodiazepine; CGI-S = Clinical Global Impression – Severity; C-SSRS = Columbia-Suicide Severity Rating Scale; ECG = electrocardiogram; ET = Early Termination; IMP = investigational medicinal product; mCIWA-B = Modified Clinical Institute Withdrawal Assessment – Benzodiazepines; PGI-C = Patient Global Impression of Change.

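### No pregnancy test is scheduled after treatment ends: Visit 17 has none, although the protocol asks for monthly tests throughout the trial

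*Protocol*

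**What the plan says.** - **Frequency.** Protocol Section 8.4.5: "At a minimum, monthly pregnancy tests will be completed throughout the trial for all women of" childbearing potential. The footnotes to the test row in Tables 2 and 3 (h and g) repeat it with no stop point: "Monthly pregnancy tests will be required for all women of childbearing potential". Neither place defines a month.
- **Collection of pregnancies.** Section 8.4.5: details "will be collected after the start of IMP and until the final contact at Visit 17". Section 4.4 counts the Visit 17 assessments as part of completing the trial.
- **Timing of Visit 17.** Section 4.1, Follow-up Period: "A Post-treatment Follow-up Visit will be made approximately 4 weeks after last dose of IMP". For subjects who stop without tapering, Section 7.3 says: "If the taper will not be utilized, then all assessments required at Visit 17 should be conducted approximately 30 days following the last dose".
- **The grid.** Table 3 marks the test at Visits 13, 14, 15/ET and 16. The Day 407 contact and Visit 17 are blank. The row "Urine pregnancy test" in SAP Table 10 (SAP Section 9.1) has the same pattern.
- **Which text governs.** Appendix 2 (Section 10.2) and Table 8 tie the required tests to the time points in the Schedule of Assessments, with further tests as needed.

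**The concern.** Section 2.3 names fetal toxicity as an important potential risk and relies on contraception and regular pregnancy testing to limit it. The last marked test falls at about the last dose, when a recent conception cannot yet show. A site that works from the grid would do no later test. Conceptions in roughly the last two weeks on drug and in early follow-up would then come to light only through the footnote, a test on suspicion, the birth control review or the subject's own report.

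A pregnancy found during the trial is followed to its outcome (Appendix 4). After Visit 17, collection stops and investigators need not seek pregnancy-related serious events. What is at stake is therefore the detection and follow-up of exposed pregnancies. Exposure itself would not change, because no study drug is left to stop at Visit 17.

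**Working it through.** **Reproducing the schedule.** The marked test days are 1, 15, then every 28 days to 379 ((379 − 15)/28 = 13 intervals), then 400. That makes 16 tests with a longest gap of 28 days. Visit 17 follows Visit 16 by 428 − 400 = 28 days = 4.0 weeks, which agrees with Section 4.1. On the grid's own 28-day spacing, a test falls due at Visit 17.

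**Visit windows (±3 days).** If both visits move freely within the grid windows, the interval runs from 425 − 403 = 22 to 431 − 397 = 34 days. Assuming independent days spread evenly over 7 × 7 = 49 combinations:
- more than 30 days: 4 + 3 + 2 + 1 = 10 of 49 (20%)
- more than 31 days: 3 + 2 + 1 = 6 of 49 (12%)

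If Visit 17 is instead timed from the actual last dose and that dose moves with Visit 16, the range is 28 ± 3 = 25 to 31 days. Then 1 of 7 (14%) exceeds 30 days and none exceeds 31.

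**What a Visit 17 test would add after a taper.** The lag from conception to a positive urine test is an assumption. The contraception period ends 30 days after the last dose (Section 5.1, criterion 2), so at Day 430.

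| Lag (days) | Day 400 test reaches conceptions to | Day 428 test reaches conceptions to | Added on-drug days | Added post-dose days | Days to 430 still uncovered |
|---|---|---|---|---|---|
| 10 | 390 | 418 | 10 | 18 | 12 |
| 14 | 386 | 414 | 14 | 14 | 16 |
| 16 | 384 | 412 | 16 | 12 | 18 |

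**Without taper.** Assume the early termination test is done at about the last dose and Visit 17 is 30 days later. With a 14-day lag, the test adds 14 on-drug days and 30 − 14 = 16 post-dose days, and leaves 14 days uncovered. With lags of 10 and 16 days, it adds 10 and 16 on-drug days and 20 and 14 post-dose days, and leaves 10 and 16 days uncovered.

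**Dose in the added on-drug days.** Protocol Table 4 starts the taper on Day 380. In weekly steps from 25 mg BID the daily dose is 35 mg (Days 380–386), 20 mg (387–393) and 10 mg (394–400).
- Taper, 14-day lag: 7 × 20 + 7 × 10 = 210 mg. At 10 days: 3 × 20 + 7 × 10 = 130 mg. At 16 days: 2 × 35 + 7 × 20 + 7 × 10 = 280 mg.
- No taper at 50 mg/day: 14 × 50 = 700 mg (10 × 50 = 500; 16 × 50 = 800).

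These are the woman's intake over the whole added period. For conceptions spread evenly over the 14 days, the mean dose from conception onward is (20 × 28 + 10 × 77)/14 = 95 mg with taper and 50 × 105/14 = 375 mg without. The factors 28, 77 and 105 are the sums of the day numbers 1–7, 8–14 and 1–14.

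**Expected number.** Assume that 30% to 50% of the approximately 120 subjects (Section 9.2) are women of childbearing potential, so 36 to 60, with 1% to 5% conceptions per woman-year.
- All 28 added days: 36 × 28/365 × 0.01 = 0.03 to 60 × 28/365 × 0.05 = 0.23.
- The 14 on-drug days alone: half of that, about 0.014 to 0.115.

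**The case against.** The strongest reply is that the requirement is already there. The monthly footnote is attached to this very row and is part of the Schedule, and Section 8.4.5 says the same. On that view only a mark is missing. If a month means a calendar month, the next test falls due at about Day 430 or 431, after the nominal Visit 17, and nothing is breached. The other safeguards are real: birth control is reviewed at the Day 407 contact and at Visit 17, a test may be done on suspicion, and related post-trial events are still reported if the investigator learns of them. The expected yield is far below one pregnancy, and a change to the Schedule is a protocol amendment.

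Much of this stands. The text can be read to require a follow-up test, the yield is small, and the milligram totals are about twice the mean dose after conception. It does not remove the point. If the text requires the test, the grid conflicts with it. If it does not, no scheduled test follows treatment. The remote-test option in Section 8.4.5 does not clearly help, because it is for periods without monthly visits and Visit 17 is itself a scheduled visit four weeks after Visit 16. Birth control is also reviewed at every earlier clinic visit, and the plan still tests at each of them.

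**Conclusion.** The concern holds. No pregnancy test is marked after Visit 16, or after early termination without taper, while the text asks for monthly tests throughout the trial and collects pregnancies to Visit 17. Whether a test is strictly overdue at Visit 17 depends on the undefined month; that none is scheduled after treatment does not.

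With a 14-day lag, a Visit 17 test would reach 28 more days of possible conception after a taper and 30 without one, 14 of them on drug in either case. The expected count depends on the assumed share of women and conception rate, which the documents do not give. The benefit is better detection and follow-up for a named risk. No exposure, endpoint or analysis is affected.

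**What to change.** Mark the urine pregnancy test in the Visit 17 column of Protocol Table 3, state that it also applies when Visit 17 is done about 30 days after the last dose without taper, and carry the mark to SAP Table 10. The number of scheduled tests goes from 16 to 17 and the longest gap stays at 28 days. The test would find conceptions up to about two weeks before Visit 17, so it does not cover the whole 30-day contraception period.

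The cost is one urine dipstick per woman of childbearing potential, at a clinic visit where safety blood is already drawn, plus a line in a protocol amendment. That amendment needs ethics committee approval (Section 10.1.1), and re-consent if the consent form changes (Section 10.1.3), so it is best combined with another amendment. The SAP edit only keeps the copied table in step.

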#### **8.4.6 Adverse Events of Special Interest**

##### **8.4.6.1 Adverse Events Potentially Related to Abuse or Dependence**

A key objective of the Abuse Potential Monitoring Plan (APMP) is to monitor for instances of abuse or diversion of the trial medication and other psychoactive substances.

In addition to monitoring for irregularities in medication handling, AEs that may be suggestive of a developing abuse issue will also receive special attention. As part of the APMP, medication handling irregularities (MHIs) must be reported, and AEs related to abuse potential and AEs involving MHIs must be reported as AEs of special interest (AESIs) with 24 hours to the sponsor with detailed narratives.

Investigators and site staff at each trial site will be trained on reporting potentially abuse related AEs (eg, recording a description of the event in the subject's own words in the source documents as well as the eCRF, in addition to the clinical term, and to be aware that a subject's report may encompass more than one event and that these should be recorded separately). The investigators will be provided with examples of potentially abuse-related AEs and trained on how to handle such events (eg, additional monitoring).

While the investigators will be provided with examples of AE terms as a guide during trial conduct, the analysis of potentially abuse-related AEs by the sponsor will be based on a search of all relevant Medical Dictionary for Regulatory Activities (MedDRA) terms, all verbatim terms, and any open text fields within the AE data to identify text strings suggestive of abuse potential, in line with the 2017 Food and Drug Administration guidance ([Guidance for Industry, 2017](#)). Refer to the separate APMP documentation for complete details on MHIs and events subject to additional monitoring (ESAMs), including documenting and reporting procedures, examples of potentially abuse-related AE terms that meet the criteria for ESAM reporting, and guidance for the training of investigators and trial site staff.

The following AEs are considered indicative of potential abuse for the CVL-865 mechanism of action:

- Abnormal behavior
- Abnormal dreams
- Amnesia
- Any reports of altered perception or hallucinations

- Apathy
- Balance disorder
- Cognitive disorder
- Depressed level of consciousness
- Depressed mood
- Dizziness
- Euphoric mood
- Feeling drunk
- Feeling of relaxation
- Sedation
- Somnolence

Narratives will be completed for the above terms; information included in the narratives will consist of time to onset/offset, time course of severity, all concurrent events, concurrent medications, and time of onset of events relative to ingestion of IMP.

#### **8.4.6.2      *Hematologic Abnormalities***

The occurrence of any of the following hematologic abnormalities must be reported as AESI to the sponsor with 24 hours and the clinical course must be discussed with the medical monitor. Management of AESIs should follow instructions described in [Table 7](#).

- Hemoglobin: females <10 g/dL; males <11 g/dL
- WBC count <3.0  $\times$  10^9/L
- Neutrophil count <2.0  $\times$  10^9/L
- Platelet count <150  $\times$  10^9/L

Treatment with study drug must be discontinued if a subject develops any of the following hematologic abnormalities and should be managed as described in [Table 7](#):

- Hemoglobin <8 g/dL
- WBC count <2.5  $\times$  10^9/L
- Neutrophil count <1.5  $\times$  10^9/L
- Platelet count <100  $\times$  10^9/L

**Table 7 Management of Hematologic Abnormalities**

Hematologic Abnormalities	Management
Hemoglobin: females <10 g/dL; males <11 g/dL	Concomitant therapies and medical history should be reviewed
WBC count <3.0 × 10  /L	CBC should be rechecked regularly until CBC returns to near baseline value
Neutrophils <2.0 × 10  /L	The finding must be reported as an AESI and must be discussed with the medical monitor
Platelet count <150 × 10  /L	
Hemoglobin <8 g/dL	Treatment with study drug should be permanently discontinued
WBC count <2.5 × 10  /L	Concomitant therapies and medical history should be reviewed
Neutrophils <1.5 × 10  /L	CBC should be rechecked regularly until CBC returns to near baseline value
Platelet count <100 × 10  /L	The finding must be reported as an AESI and must be discussed with the medical monitor

Abbreviations: AESI = adverse event of special interest; CBC = complete blood count; WBC = white blood cell

#### 8.4.6.3 Abnormal Liver Function Tests

The finding of an elevated alanine aminotransferase (ALT) or aspartate aminotransferase (AST) >3 × upper limit of normal range (ULN) in combination with either an elevated total bilirubin >2 × ULN or clinical jaundice in the absence of cholestasis or other causes of hyperbilirubinemia is considered to be an indicator of severe liver injury. Therefore, investigators must report the occurrence of either of the following as an AESI to the sponsor with 24 hours:

- Treatment-emergent ALT or AST >3 × ULN and total bilirubin >2 × ULN
- Treatment-emergent ALT or AST >3 × ULN in combination with clinical jaundice

#### 8.5 Treatment of Overdose

For this trial, any dose of CVL-865 greater than 80 mg within a 24-hour time period (+2 hours) will be considered an overdose.

There is no specific antidote for overdose with CVL-865. Treatment of overdose should consist of general supportive measures. In the event of an overdose, the investigator should complete the following:

1. Contact the medical monitor immediately.
2. Closely monitor the subject for any AE/SAE and laboratory abnormalities until CVL-865 can no longer be detected systemically (at least 3 days).
3. Document the quantity of the excess dose as well as the duration of the overdose in the eCRF.

Decisions regarding dose interruptions or modifications will be made by the investigator in consultation with the medical monitor based on the clinical evaluation of the subject.

## 8.6 Pharmacokinetics

### 8.6.1 *Blood Samples for CVL-865 Concentrations*

Samples for determination of CVL-865 concentrations will be collected in appropriately labeled tubes as specified in the Schedule of Assessments ([Table 2](#) and [Table 3](#)). Additional instructions are provided in the Laboratory Flow Chart.

### 8.6.2 *Blood Samples for Anti-epileptic Drug Concentrations*

Samples for determination of concentrations of adjunctive AEDs will be collected in appropriately labelled tubes as specified in the Schedule of Assessments ([Table 2](#) and [Table 3](#)). Additional instructions are provided in the Laboratory Flow Chart.

### 8.6.3 *Methods and Analysis*

Additional details regarding the collection, processing, storage, and shipping of all pharmacokinetic (PK) plasma samples will be provided in a laboratory manual. All plasma samples will be analyzed for analyte using a validated bioanalytical method. CVL-865 plasma samples collected in this trial may be used for other exploratory purposes, eg, method development, identification of metabolites and metabolite scouting. Results of such analyses will not be reported in the Clinical Study Report (CSR).

